Maastricht Ankylosing Spondylitis Enthesitis Score (MASES)	The MASES is an index used to measure the severity of enthesitis (Heuft-Dorenbosch et al. 2003). The MASES assesses 13 sites for enthesitis using a score of “0” for no activity, or “1” for activity. Sites assessed include: costochondral 1 (right/left), costochondral 7 (right/left), spinal iliaca anterior superior (right/left), crista iliaca (right/left),	MASES	The MASES is the sum of all site scores. Range: 0 to 13, higher scores indicate more severe enthesitis 0 = no activity and not evaluable 1 = activity	Missing if >20% (ie, ≥ 3) sites are missing. If $\leq 20\%$ missing, then imputed sum = sum of scores from nonmissing sites x 13/ no. of nonmissing sites
		MASES change from baseline	Calculated as: observed MASES – baseline MASES	Missing if baseline or observed value is missing
		MASES score = 0	MASES score = 0 refers to complete resolution in enthesitis. Analysis of MASES score = 0 only applies to patients with baseline enthesitis (MASES >0).	Missing if observed value is missing

Measure	Description	Variable	Derivation / Comment	Imputation Approach if with Missing Components
	spinal iliaca posterior (right/left), processus spinosus L5, and Achilles tendon proximal insertion (right/left).			
Spondyloarthritis Research Consortium of Canada (SPARCC) enthesitis	SPARCC enthesitis is an index used to measure the severity of enthesitis (Maksymowych et al. 2009). The SPARCC assesses 16 sites for enthesitis using a score of “0” for no activity, or “1” for activity. Sites assessed include Medial epicondyle (left/right [L/R]), Lateral epicondyle (L/R), Supraspinatus insertion into greater tuberosity of humerus (L/R), Greater trochanter (L/R), Quadriceps insertion into superior border of patella (L/R), Patellar ligament insertion into inferior pole of patella or tibial tubercle (L/R), Achilles tendon insertion into calcaneum (L/R), and Plantar fascia insertion into calcaneum (L/R).	SPARCC enthesitis	The SPARCC is the sum of all site scores Range: 0–16, higher scores indicate more severe enthesitis.	Missing if >20% (ie, ≥4) sites are missing. If ≤20% missing, then imputed sum = sum of scores from nonmissing sites x 16/ no. of nonmissing sites.
		SPARCC enthesitis change from baseline	Calculated as: observed SPARCC enthesitis – baseline SPARCC enthesitis	Missing if baseline or observed value is missing

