		SPARCC enthesitis score = 0	SPARCC enthesitis score = 0 refers to complete resolution in enthesitis. Analysis of SPARCC enthesitis score = 0 only applies to patients with baseline enthesitis (SPARCC enthesitis >0).	Missing if observed value is missing
Tender Joint Count (TJC)	The number of tender and painful joints will be determined by examination	TJC total score	Adjusted sum of the pain/tenderness for all 46 joints:	If more than half of the joint scores are non-evaluable, the total score will be missing.

Measure	Description	Variable	Derivation / Comment	Imputation Approach if with Missing Components
	of 46 joints (23 joints on each side of the patient's body). The 46 joints are assessed and classified as tender or not tender		$\left(\frac{\text{sum of all joints checked to be painful/tender}}{\text{number of evaluable joints}} \right) \times 46$ 
See Appendix 4 for details.
	

Measure	Description	Variable	Derivation / Comment	Imputation Approach if with Missing Components
		TJC change from baseline	Calculated as: observed TJC – baseline TJC only applies to patients whose baseline TJC >0.	Missing if baseline or observed value is missing
		Proportion of patients with TJC = 0 when baseline TJC >0	TJC >0 refers to incidence of TJC. Analysis of TJC = 0 only applies to patients whose baseline TJC >0.	Missing if observed value is missing
Swollen Joint Count (SJC)	The number of swollen joints will be determined by examination of 44 joints (22 joints on each side of the patient’s body). The 44 joints are assessed and classified as swollen or not swollen.	SJC total score	Adjusted sum of the pain/tenderness for all 44 joints. $\left(\frac{\text{sum of all joints checked to be swollen}}{\text{number of evaluable joints}} \right) \times 44$ See Appendix 4 for details.	If more than half of the joint scores are nonevaluable, the total score will be missing.
		SJC change from baseline	Calculated as: observed SJC – baseline SJC Only applies to patients whose baseline SJC >0.	Missing if baseline or observed value is missing
		Proportion of patients with SJC = 0 when baseline SJC >0	SJC >0 refers to incidence of SJC. Analysis of SJC = 0 only applies to patients whose baseline SJC >0.	Missing if observed value is missing

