	MASES score = 0 (similarly SPARCC = 0)	Logistic regression analysis with NRI; Fisher's exact test with NRI	ITT Population with Baseline MASES >0 (or SPARCC >0)	IXE80Q2W & IXE80Q4W vs. placebo at Week 16 and all other postbaseline visits in Period 2	Other secondary efficacy analyses (Section 6.10.4).
		Descriptive statistics of MASES = 0 (or SPARCC=0)	Extended Treatment Period Population with Baseline MASES >0 (or SPARCC >0)	No treatment group comparisons during Period 3	Other secondary efficacy analyses (Section 6.10.4).
Peripheral Arthritis	TJC and SJC change from baseline	MMRM	ITT Population with baseline TJC >0 (or SJC >0)	IXE80Q2W & IXE80Q4W vs. placebo at Week 16 and all other postbaseline visits in Period 2	Other secondary efficacy analyses (Section 6.10.4).
		ANCOVA with mBOCF	ITT Population with baseline TJC >0 (or SJC >0)	IXE80Q2W & IXE80Q4W vs. placebo at Week 16 and all other postbaseline visits in Period 2	Other secondary efficacy analyses (Section 6.10.4).
		Descriptive statistics of change from baseline	Extended Treatment Period Population with baseline TJC >0 (or SJC >0)	No treatment group comparisons during Period 3	Other secondary efficacy analyses (Section 6.10.4).
	TJC = 0 (similarly, SJC = 0)	Logistic regression analysis with NRI; Fisher's exact test with NRI	ITT Population with Baseline TJC >0 (or SJC >0)	IXE80Q2W & IXE80Q4W vs. placebo at Week 16 and all other postbaseline visits in Period 2	Other secondary efficacy analyses (Section 6.10.4).

Measure	Variable	Analysis Method (Sections 6.1, 6.3)	Population (Section 6.1.5)	Comparison/Time Point	Analysis Type
		Descriptive statistics of TJC = 0 (or SJC =0)	Extended Treatment Period Population with Baseline TJC >0 (or SJC >0)	No treatment group comparisons during Period 3	Other secondary efficacy analyses (Section 6.10.4).
Anterior uveitis	Crude and exposure-adjusted incidence rates for patients with anterior uveitis	Fisher’s exact test and Poisson regression	ITT Population	IXE80Q2W & IXE80Q4W vs. placebo during Period 2	Other secondary efficacy analyses (Section 6.10.4).
		Descriptive statistics	Extended Treatment Period Population	No treatment group comparisons during Period 3	Other secondary efficacy analyses (Section 6.10.4).
		Descriptive statistics	ITT Population Who are Initially Randomized to Ixekizumab	No treatment group comparisons during Combined Periods 2 and 3	Other secondary efficacy analyses (Section 6.10.4).

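### MASES scores a non-evaluable site as inactive, so the same row's rule for missing sites never counts it

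*SAP*

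**What the plan says.** The MASES row of SAP Table RHBV.6.4 (Section 6.10) sums 13 sites: "Range: 0 to 13, higher scores indicate more severe enthesitis". Its derivation cell gives the code as "0 = no activity and not evaluable". Its cell on missing components says "Missing if >20% (ie, ≥ 3) sites are missing"; with fewer missing, "imputed sum = sum of scores from nonmissing sites x 13/ no. of nonmissing sites". For the responder variable, "MASES score = 0 refers to complete resolution in enthesitis".

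Table RHBV.6.5 analyses the change by MMRM and by ANCOVA with mBOCF. It analyses a score of 0 by logistic regression and Fisher's exact test with nonresponder imputation (NRI). Both use ITT patients whose baseline MASES is above 0. Under SAP Section 6.3.1, missing response data count as nonresponse.

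Neighbouring text treats unassessed sites differently:

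- Protocol Section 8.1.2.10 uses 0 for no activity only and does not mention non-evaluable sites.
- The SPARCC enthesitis row, also scored 0 or 1 per site, has "imputed sum = sum of scores from nonmissing sites x 16/ no. of nonmissing sites" and no code for non-evaluable sites.
- The joint counts divide by the number of evaluable joints, and the tender joint row adds "If more than half of the joint scores are non-evaluable, the total score will be missing".

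The SAP revision history (Section 3) lists the handling of non-evaluable MASES sites among the clarifications made since Version 1. Version 2 was approved before first unblinding. No reason for the choice is given.

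**The concern.** A site that nobody could assess receives the best possible value. Because 0 is a nonmissing value, the missing-site rule in the next cell acts only on sites left blank. Two patients with the same information can then be scored differently, depending on whether the site was left blank or recorded as not evaluable.

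Two results are at stake. The change from baseline takes in an error that comes from lack of assessment. The responder endpoint can record complete resolution for a patient in whom much of the index was not examined, although NRI was chosen for that endpoint so that absent information counts against response.

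**Working it through.** **Inputs.** 13 sites, scored 0 or 1; proration by 13 over the number of nonmissing sites; score missing at 3 or more missing sites (all from the MASES row). Let k be the number of non-evaluable sites and a the number of active sites among those evaluated.

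**The plan's own threshold.** 2/13 = 15.4%, not above 20%; 3/13 = 23.1%, above 20%. The stated limit of 3 reproduces. So does the limit of 4 in the SPARCC row: 3/16 = 18.75%, 4/16 = 25%.

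**Score at one visit.** Zero coding gives a. The row's missing-site rule gives a × 13/(13 − k) for k = 1 or 2, and missing for k ≥ 3. When a > 0, the ratio of the first to the second is (13 − k)/13, so zero coding is lower by k/13: 7.7% for k = 1 and 15.4% for k = 2.

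| k | a | Zero coding | Missing-site rule |
|---|---|---|---|
| 1 | 3 | 3 | 3 × 13/12 = 3.25 |
| 2 | 3 | 3 | 3 × 13/11 = 3.55 |
| 2 | 5 | 5 | 5 × 13/11 = 5.91 |
| 1 or 2 | 0 | 0 | 0 |
| 3 or more | any | a | missing |

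**Change from baseline.** Three invented cases, each with two non-evaluable sites:

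1. Non-evaluable only after baseline: 5 active of 13 at baseline, 3 active of 11 evaluable at Week 16. Zero coding: 3 − 5 = −2.00. Rule: 3.55 − 5 = −1.45. Zero coding shows more improvement.
2. Non-evaluable only at baseline: 5 active of 11, then 3 active of 13. Zero coding: 3 − 5 = −2.00. Rule: 3 − 5.91 = −2.91. Zero coding shows less improvement.
3. Non-evaluable at both visits: 5 active of 11, then 2 active of 11. Zero coding: 2 − 5 = −3.00. Rule: (2 − 5) × 13/11 = −3.55. Zero coding again shows less improvement.

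In addition, a patient whose only active site is non-evaluable at baseline scores 0 and leaves the baseline MASES >0 set. Proration does not rescue that patient, because 0 × 13/12 = 0.

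**Score of 0.** With k = 1 or 2 and a = 0, both rules give 0 and the patient is a responder either way. With k ≥ 3 and a = 0, zero coding gives 0 and a responder; the missing rule with NRI gives a nonresponder. In the extreme, 13 non-evaluable sites give a score of 0.

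**The case against.** The coding is a deliberate choice, fixed before unblinding. The row can be read as treating not evaluable and missing as separate states, and nothing in the documents says that a non-evaluable MASES site must count as missing. That stands as a description of the text. It supplies no reason, however, for giving an unassessed site the best value, nor for differing from the protocol's meaning of 0.

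A reader might infer that the coding pushes results toward improvement, or favours ixekizumab. The documents support neither. The three cases above show that the error in change from baseline can go either way. Patients and site personnel are blinded, and nothing suggests that non-evaluable sites would be more common in one arm.

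The joint counts are only a partial comparator. They drop non-evaluable joints from the denominator, but go missing only when more than half are non-evaluable, so they do not support a 20% limit. The protocol also gives reasons why joints become non-evaluable (replacement, ankylosis, arthrodesis, injection) and gives none for entheseal sites.

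Finally, proration alone does not protect the resolution endpoint when one or two sites are non-evaluable. That is correct, and SPARCC = 0 and the joint counts of 0 share the property.

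**Conclusion.** The point holds as an inconsistency within one table row, with a small, bounded effect. Relative to the row's own missing-site rule, a nonzero score is 7.7% lower with one non-evaluable site and 15.4% lower with two. With three or more, a score is reported where the rule gives none, and an NRI nonresponder can become a resolution responder.

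These percentages compare two scoring rules. They measure error against the true score only if a non-evaluable site is as likely to be active as the evaluated ones, which proration assumes and the documents do not establish. The number of non-evaluable sites is not given, so the effect on any estimate is unknown and may be negligible.

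MASES is an other secondary endpoint without multiplicity adjustment (SAP Section 6.10.4). ASAS40 and the major secondary outcomes are untouched. This is a worthwhile correction, not a threat to the trial's conclusions.

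**What to change.** - In the MASES row, reserve 0 for no activity and treat not evaluable as a missing site, so that the existing proration and 20% rule apply.
- Because proration still gives 0 when one or two sites are non-evaluable and none is active, do not count a score of 0 as resolution at a visit where a site active at baseline is non-evaluable. This second rule is new; the SAP applies nothing like it to the other counts.
- If the present coding is kept, state why, and report the number of non-evaluable sites by arm and visit.

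The derivation change is about one line, and the resolution rule needs a check against the baseline sites. The price is a few more missing scores or nonresponders. The change does not recover patients who fall outside the baseline MASES >0 set because their only active site could not be assessed.

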
Other secondary objectives are:
 
 
• To compare both ixekizumab regimens (80 mg Q2W or 80 mg Q4W) to placebo during the 16-week placebo controlled period (Period 2)
 
	
 
• Proportion of patients who achieve ASAS20, ASAS40, ASAS 5/6, and partial remission by ASAS criteria
 
• Change from baseline in the individual components of the ASAS criteria
 
• Change from baseline in BASDAI
 
• Proportion of patients reaching BASDAI50
 
• Change from baseline in ASDAS
 
• Proportion of patients who experience clinically-important improvement (change of ASDAS from baseline <math>\geq 1.1</math>), major improvement (change of ASDAS from baseline <math>\geq 2.0</math>), or inactive disease (ASDAS score <math>< 1.3</math>)
 
• Change from baseline in the measure of high sensitivity C-reactive protein (CRP)
 
• Change from baseline in BASFI
 
• Change from baseline in mobility               
 
○ Bath Ankylosing Spondylitis Metrology Index (BASMI) (linear) and individual components
 
○ Chest expansion
 
○ Change from baseline in occiput to wall distance
 
 
 
• Change from baseline in MRI of the SIJ (SPARCC score)
 
• Change from baseline in SPARCC SIJ Structural Score (SSS)
 
• Change from baseline in MRI of the spine (Ankylosing Spondylitis Spinal Magnetic Resonance Imaging activity–Berlin Score [ASSpiMRI-Berlin])
 
• Change from baseline in Maastricht Ankylosing Spondylitis Enthesitis Score (MASES)
 
• Change from baseline in SPARCC Enthesitis Score
 
• Incidence and severity of peripheral arthritis by tender (TJC) and swollen joint count scores (SJC) of 46/44 joints.
 
• Incidence rate of anterior uveitis or uveitis flares
 
• Change from baseline in the following health outcomes measures: Fatigue NRS score, ASAS-HI score, Jenkins Sleep Evaluation Questionnaire (JSEQ), Work Productivity Activity Impairment—Spondyloarthritis (WPAI-SpA) scores, SF-36 (both PCS and mental component scores [MCS]) and Quick Inventory of Depressive Symptomatology—Self Report 16 items (QIDS-SR16) score.
 

Objectives	Endpoints
Secondary objectives continued	

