6.10.4. Other Secondary Efficacy Analyses

There will be no adjustment for multiple comparisons for other secondary efficacy analyses.

The other secondary efficacy variables for secondary objectives include:

- ASAS40: analyses other than primary analysis (Section 6.10.1) and additional analysis of the primary outcome (Section 6.10.3)
- ASAS20: analyses other than major secondary efficacy analysis (Section 6.10.2)
- ASAS5/6 and partial remission
- ASDAS<2.1: ad hoc analysis post interim 1 database lock
- Change from baseline in individual components of the ASAS criteria (patient global, spinal pain, function [see BASFI below], inflammation [see BASDAI below], CRP [see CRP below], and spinal mobility (lateral spinal flexion) [see BASMI below])
- Change from baseline in BASDAI and inflammation (mean of Q5 and Q6 on BASDAI)
- BASDAI 50: analyses other than major secondary efficacy analysis (Section 6.10.2)
- Change from baseline in ASDAS: analyses other than major secondary efficacy analysis (Section 6.10.2)
- ASDAS inactive disease: analyses other than major secondary efficacy analysis (Section 6.10.2)
- ASDAS disease activity states: inactive disease, low disease activity, high disease activity, very high disease activity; clinically important improvement and major improvement
- Change from baseline in CRP
- Change from baseline in BASFI: analyses other than major secondary efficacy analysis (Section 6.10.2)
- Change from baseline in mobility (BASMI linear and individual components, chest expansion, occiput to wall distance)
- Change from baseline in MRI SPARCC spine score: analyses other than major secondary efficacy analysis (Section 6.10.2)
- Change from baseline in MRI SPARCC SIJ structural score (SSS) for each of the 4 features: fat metaplasia, bone erosion, backfill and ankylosis.
- Change from baseline in MRI ASSpiMRI –Berlin score
- Change from baseline in MRI SPARCC SIJ score
- Change from baseline in enthesitis score (MASES and SPARCC)
- Change from baseline in TJC and SJC scores
- Incidence of peripheral arthritis by TJC and SJC scores of 46/44 joints.
- Incidence rate of anterior uveitis or uveitis flares
- Change from baseline in ASAS-NSAID score (apply to Period 3 analysis only), Section 6.10.4.1.

Treatment comparisons of each ixekizumab treatment group and placebo, as well as adalimumab treatment group and placebo at Week 16 (Visit 8) and all other postbaseline visits during Period 2 will be provided.

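### Incidence of peripheral arthritis is a listed endpoint, but every post-baseline TJC or SJC row in the analysis table excludes patients whose baseline value of that count is 0

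*SAP*

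**What the plan says.** The endpoint appears in three places. Protocol Table RHBV.1 lists, among the other secondary endpoints for ixekizumab against placebo in Period 2, "Incidence and severity of peripheral arthritis by tender (TJC) and swollen joint count scores (SJC) of 46/44 joints". SAP Section 4 repeats it. SAP Section 6.10.4 lists "Incidence of peripheral arthritis by TJC and SJC scores of 46/44 joints" as its own item, next to a separate item for change from baseline in the two counts. None of the three states a restriction by baseline count.

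SAP Table RHBV.6.4 then gives the derivations. For tender joints it says "TJC >0 refers to incidence of TJC" and immediately adds "Analysis of TJC = 0 only applies to patients whose baseline TJC >0". For swollen joints the pattern is the same: "Analysis of SJC = 0 only applies to patients whose baseline SJC >0". Change from baseline in TJC also "only applies to patients whose baseline TJC >0", with matching wording for SJC.

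SAP Table RHBV.6.5 carries the restriction into every analysis row. Period 2 rows use the ITT patients with a positive baseline value of the count concerned. The Period 3 summaries use the Extended Treatment Period patients with the same condition. The closing text of Section 6.10.4 makes this table the detailed specification for the other secondary outcomes.

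**The concern.** Incidence, on its ordinary meaning, concerns patients who do not have the condition at the start. A proportion reaching a count of 0 among patients who began above 0 is resolution. The two quantities have different denominators and can move independently, so one cannot stand in for the other.

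At stake is a labelling risk and a gap. A resolution result could be reported under an endpoint named incidence. And a difference between arms in newly tender or swollen joints would not appear in the outputs specified for this endpoint.

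**Working it through.** The plan states no figure for this endpoint, so the check is a trace of the endpoint through the documents, followed by an illustration.

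**Trace**

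1. Objective: incidence and severity by TJC/SJC, no baseline restriction (Protocol Table RHBV.1; SAP Section 4).
2. Variable list: incidence is an item separate from change in TJC/SJC (SAP Section 6.10.4). It is therefore not another name for change.
3. Definition: count >0 is called incidence (SAP Table RHBV.6.4).
4. Binary variable derived: count = 0 given baseline count >0 (same table). Within that group, count = 0 is resolution and count >0 is persistence. Neither is onset. Nor is the complement a whole-population prevalence, because patients starting at 0 are not in the denominator.
5. Analysis rows (SAP Table RHBV.6.5, Peripheral Arthritis):

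| Row | Period | Restricted to baseline count >0 |
|---|---|---|
| Change, MMRM | 2 | yes |
| Change, ANCOVA with mBOCF | 2 | yes |
| Change, descriptive | 3 | yes |
| Count = 0, logistic regression and Fisher's exact test with NRI | 2 | yes |
| Count = 0, descriptive | 3 | yes |

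Five of five rows are restricted.

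6. Contrasts within Table RHBV.6.4. Enthesitis uses the same construction, but a MASES of 0 is described as complete resolution. Anterior uveitis, which is also an incidence endpoint, is summarized separately for patients with and without a prior history. Only peripheral arthritis names incidence and leaves out the patients who start at 0.
7. The one unrestricted joint-count summary is in the baseline characteristics (SAP Section 6.7.1), which counts ITT patients with any tender or any swollen joint at entry. That is prevalence at entry.

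**Illustration (assumed inputs)**

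Patients per arm: 80 (SAP Section 5.3). Share with a baseline value of 0 on a given count, s: not in the documents; assumed 30%, 50% and 70%.

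Patients per arm outside the rows for that count: 80 × s = 24, 40 and 56.

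Suppose two arms have the same resolution, 40%, but onset o of 5% and 15% in patients starting at 0 (all assumed). The planned count = 0 analysis compares 40% with 40%. Whole-arm prevalence at Week 16 is (1 − s) × 0.60 + s × o:

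- s = 30%: 0.42 + 0.015 = 43.5% against 0.42 + 0.045 = 46.5%
- s = 50%: 0.30 + 0.025 = 32.5% against 0.30 + 0.075 = 37.5%
- s = 70%: 0.18 + 0.035 = 21.5% against 0.18 + 0.105 = 28.5%

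The planned rows would show none of this.

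Precision of an added emergence summary, for a 10% rate in one arm: half-width of the 95% interval = 1.96 × √(0.10 × 0.90 / (80 × s)), which gives 12.0, 9.3 and 7.9 percentage points. Such a summary would be mainly descriptive.

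**The case against.** Several points can fairly be made for the plan.

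- **Section 6.10.4 already promises the comparison.** It says each ixekizumab arm and adalimumab will be compared with placebo at Week 16 and the other Period 2 visits for the listed variables, with no baseline restriction. That stands as a commitment. But the table that the same section makes the detailed specification has no row for it. The accurate description is a mismatch between text and table, not a plan that rules the analysis out.
- **Incidence may have been meant loosely, as presence.** The documents do not say new onset. Even so, presence would need all patients in the denominator, and those starting at 0 are still left out.
- **The restriction was deliberate.** The SAP revision history records that Version 2, approved before first unblinding, updated the population for these analyses. That is sensible for change and resolution. It does not supply an incidence analysis.
- **New arthritis could be seen elsewhere.** New conditions are recorded as adverse events, and BASDAI question 3 on peripheral joints feeds scores analysed in the full ITT population. Those are not the TJC/SJC endpoint named in the objective, but they do limit the consequence to that endpoint.
- **A baseline count of 0 does not mean no previous arthritis.** Past synovitis is a qualifying feature in Protocol Appendix 5, and the SAP records history of arthritis. An added summary would mix first onset with recurrence. This stands, and it governs how the summary should be named.

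A reader might infer that most of the trial population contributes nothing to this endpoint. The documents do not support that. They give no share with a count of 0, and the exclusion works count by count: a patient with SJC = 0 and TJC >0 is in every TJC row. A reader might also infer that the trial cannot answer its objective. That too goes beyond the text: Protocol Appendix 2 schedules both counts at Weeks 0, 8, 16, 24, 36 and 52 without restriction by baseline count, so the data for the missing analysis are planned.

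**Conclusion.** The point holds as a mismatch between the named endpoint and its specified analyses. All five post-baseline TJC/SJC rows estimate change, resolution or persistence, and none estimates emergence of tender or swollen joints in patients with a baseline count of 0.

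The consequence is minor. This is an other secondary endpoint without multiplicity adjustment, and no primary or major secondary result depends on it. The number of patients left out is unknown; the 24 to 56 per arm shown above rests wholly on an assumed 30% to 70% and applies to one count at a time. The conclusion also takes Table RHBV.6.5 as complete for this endpoint. The redacted Appendix 4 could not be read, but it is cited only for deriving the total joint scores.

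**What to change.** Add to SAP Table RHBV.6.5 a summary by arm at Week 16 of TJC >0 among patients with baseline TJC = 0, and of SJC >0 among patients with baseline SJC = 0. Use observed counts, show missing values separately, and give Fisher's exact test without multiplicity adjustment. Present it as mainly descriptive, and call it emergence of tender or swollen joints, since it may include recurrence.

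SAP Version 3 was approved after unblinding. An addition made after the Week 16 unblinding should therefore be labelled ad hoc, as the SAP already does for ASDAS <2.1.

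Rename the existing TJC = 0 and SJC = 0 analyses as resolution, and correct the two sentences in Table RHBV.6.4 that equate a count above 0 with incidence.

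The cost is one table from joint counts already scheduled, plus wording changes.
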